We hypothesize that preterm infants supplemented with early physiologic doses of L-carnitine while on parenteral nutrition will have improved short-term growth parameters and significantly higher neurobehavioral scores when compared with control infants.

Primary Aims:

To determine whether carnitine supplementation is associated with:

- 1. Decreased percent weight loss within the first two weeks of life and decreased length of time to regain birthweight.
- 2. Improved performance on the NICU Network Neurobehavioral Scale (NNNS) at 40 weeks postmenstrual age (+/- 2 weeks).

Secondary Aims:

To determine whether carnitine supplementation is associated with:

- 1. Increased rate of growth of head circumference within the first month of life and increased food efficiency (weight gain/calorie intake) during the supplementation period.
- 2. Normalization of the serum carnitine profile at two weeks of life, compared with infants born at a post-menstrual age 2 weeks later.
- 3. Enhanced brain maturation as measured by amplitude-integrated EEG (aEEG) measurements obtained during the hospital course
- 4. Fewer abnormal findings, better brain growth, white matter development and brain metabolism on brain magnetic resonance imaging (MRI) at 36-40 weeks' corrected age (prior to hospital discharge)

Because of the potential for systemic effects of L-carnitine supplementation, we will also monitor those variables which showed significant difference in our prior study: rates of proven infection, hearing screen failure and PDA ligation.

Primary Outcomes:

- 1. Length of time to regain birthweight,
- 2. Percent weight loss in the first two weeks of life,
- 3. Neurodevelopmental scores on the NICU Network Neurobehavioral Scale (NNNS) at 40 weeks post-menstrual age (+/- 2 weeks)

Methods/Design:

This is a prospective, randomized controlled clinical trial involving infants with gestational age (GA) <32 wks who are born at either the Jack D. Weiler Hospital or the Wakefield Division of Montefiore and admitted to theirNeonatal Intensive Care Unit. Informed consent will be obtained from the parents of eligible patients as early as possible within 72 hours of birth. Infants whose parents have signed an informed consent form will be randomized to receive either carnitine supplementation (50 µmol/kg/day) versus placebo within 72-96 hours of birth.

Inclusion criteria:

- Infants born <32weeks' gestation
- Exclusion criteria:
 - Presence of

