We will assess neurodevelopmental outcomes at 18-24 months corrected age using the Bayley Scales of Infant and Toddler Development, Third Edition (BSID-III). The BSID-III is a validated instrument used for assessing the development of Cognitive, Language (Receptive and Expressive), Motor (Fine and Gross), Social-Emotional and Adaptive skills in infants and toddlers. This normative assessment yields scaled scores, composite scores, percentile ranks, and developmental age equivalents, all of which provide important information about a child's level of functioning relative to his or her same-age peers. While Cognitive, Language and Motor skills are assessed through direct interaction with the child, Social-Emotional and Adaptive skills are obtained from parent report. Because the BSID-III is commonly used for identifying children who are in need of early intervention due to developmental delays, this instrument will be sensitive to detecting the types of developmental issues we often see in very young children born preterm. Additionally, at the follow-up visit at 18-24 months corrected age, we will administer two parental questionnaires: the Modified Checklist for Autism in Toddlers (M-CHAT) and the Child Behavior Checklist (CBCL). M-CHAT is a parent-report checklist developed to screen children for early signs of autistic features. The CBCL is a standardized, well-validated parent-report questionnaire developed to assess various maladaptive behavioral and emotional problems in young children.

Record confidentiality: Records relating to the study will be kept in a secure location, to which only study personnel will have access. Records will be kept in a locked file cabinet in the neonatology offices and in a password-protected computer.

Statistical Analyses:

Statistical analysis will be performed with the assistance of a statistician.

Sample size:

We plan to recruit a total of 150 infants for our study over approximately 36months' time. This number is based upon an expected attrition of approximately 50 infants over the course of the study and a desired sample size of 100 infants. The inclusion of 100 infants in our study (50 in each study arm) will allow us to detect a moderate difference in our primary outcomes at a significance level of 0.05 with a power of 0.8. (0.5 SD; α = .05; power = .80).

Primary Outcomes	Mean	Standard Deviation	0.5 x Standard Deviation
Percent weight loss*	10.8%	6.2	3.1
Time to regain	11.3 days	4.3	2.2
birthweight*			

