The effect of L-carnitine supplementation on outcome measures in enrolled infants will be examined for significance by comparing the two groups using unpaired data analysis with the assistance of a statistician. Continuous data (percent weight loss, time to regain birthweight, NNNS score, BSID-III scores) will be compared between the "placebo" and the "carnitine supplemented" groups by unpaired student t-test (a 2 tailed P value <0.05 will be considered to indicate statistical significance) or Wilcoxon's rank sum test for non-parametric parameters. Unmatched nominal data will be compared using Fisher's Exact Test or Chi-square test as required (e.g.: presence or absence of normalization of the carnitine profile; or presence or absence of pathological findings on the discharge MRI). Logistic regression models will be used to adjust for potentially confounding factors including gestational age, birth weight, race, gender, Apgar scores.

Risks and Discomforts:

A brief description of the risks and discomforts associated with this study is included in the protocol consent form and will be discussed in detail with each family at the time of study enrollment.

Carnitine is routinely administered with parenteral nutrition in approximately one-third of the neonatal intensive care units in the United States, although not in the Jack D. Weiler Hospital or Montefiore North Division NICU's. Carnitine is FDA-approved, and there have been no reports of severe toxicity from

overdose. Data available from the adult literature reports side effects of mild gastrointestinal symptoms such as gastritis, vomiting, diarrhea or abdominal cramping; body odor; and seizures, in patients with or without a known seizure disorder. These side effects are dose-dependent and might be avoided by slow consumption of the solution or greater dilution. One investigator reported transient elevation of triglycerides and increased platelet aggregation in uremic patients with severe renal insufficiency who received high doses of carnitine supplementation.⁵²

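### For uncommon binary outcomes the planned multi-factor logistic adjustment is unstable, and it omits SGA, a randomisation stratum; a penalised fit on the stratification factors is a cheap improvement

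*Combined protocol and SAP*

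**What the plan says.** In Statistical Analyses, under Outcome Measures, yes/no outcomes are first compared without adjustment, by Fisher's exact or chi-square test. Carnitine normalisation and pathological MRI findings are the examples given. One sentence then adds: "Logistic regression models will be used to adjust for potentially confounding factors including gestational age, birth weight, race, gender, Apgar scores". The list is open-ended. The section does not say which outcomes the model serves, how race and Apgar scores are coded, or what happens when events are few.

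Other binary outcomes appear after the Secondary Aims, where the plan undertakes to monitor "rates of proven infection, hearing screen failure and PDA ligation", carried over from the earlier trial.

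On numbers, the Sample size section says "We plan to recruit a total of 150 infants for our study", allowing for "expected attrition of approximately 50 infants over the course of the study and a desired sample size of 100 infants". The Randomization section stratifies into three gestational-age bands plus a fourth SGA group, analyses by intention to treat, and takes one infant from each multiple-birth set into the analysis. No event rate is given for any binary outcome.

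**The concern.** The information in a logistic model is limited by the rarer outcome category, not by the total sample. Six or more parameters is a lot for a trial of this size if the outcome is uncommon. Sparse categories, such as a small race group, can then separate the data. The fit is reported with infinite or absurd coefficients, or does not converge, and someone must choose a simpler model after seeing the data.

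The adjusted estimate matters most for PDA ligation. Risks and Discomforts attributes the earlier excess partly to lower birth weight and greater fluid intake, so an adjusted result is likely to be wanted there. The listed adjusters also omit SGA, although the plan stratifies on it because it expects it to affect outcome.

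**Working it through.** **The plan's own figures.** 150 recruited − 50 lost = 100, or 50 per arm; this reproduces. The power statement ("0.5 SD; α = .05; power = .80") concerns the continuous primary outcomes. With "a 2 tailed P value <0.05 will be considered to indicate statistical significance", 0.5 × √(50/2) = 2.5, and Φ(2.5 − 1.96) = 0.705. The stated 0.80 needs a one-sided test: Φ(2.5 − 1.645) = 0.804. That is a separate matter. There is no figure for binary outcomes to reproduce.

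**Parameters.** Arm + gestational age + birth weight + race (two levels) + gender + one Apgar score = 6. With four race levels and two Apgar scores: 1 + 1 + 1 + 3 + 1 + 2 = 9. Coding is not stated, so 6 to 9 is an assumed range. Arm + continuous gestational age + SGA = 3.

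**Events per parameter** = N × event rate ÷ parameters. Event rates are assumptions.

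| Rate | N=100: 6 / 9 / 3 | N=150: 6 / 9 / 3 |
|---|---|---|
| 10% | 1.7 / 1.1 / 3.3 | 2.5 / 1.7 / 5.0 |
| 20% | 3.3 / 2.2 / 6.7 | 5.0 / 3.3 / 10.0 |
| 30% | 5.0 / 3.3 / 10.0 | 7.5 / 5.0 / 15.0 |
| 50% | 8.3 / 5.6 / 16.7 | 12.5 / 8.3 / 25.0 |

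**Simulation with seven terms** (arm, gestational age, birth weight, two race terms, sex, one Apgar score; 2,000 trials per cell; covariate effects assumed). Failure means that any coefficient diverged or the fit did not converge. Odds ratios are exp(mean log odds ratio) over the trials that could be fitted.

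| Rate | N=100: failed | N=100: estimate of OR 2 | N=150: failed | N=150: estimate of OR 2 |
|---|---|---|---|---|
| 10% | 18% | 2.22 | 5-6% | 2.25 |
| 20% | 1-2% | 2.25 | under 0.5% | 2.13 |
| 30% | under 0.5% | 2.17 | under 0.5% | 2.09 |
| 50% | 0% | 2.12 | 0% | 2.09 |

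At 5% events and N=100, 58-59% of fits failed. On the log scale the overstatement at N=100 is ln(2.25/2) ÷ ln 2 = 0.118/0.693 = 17% at a 20% rate, and ln(2.12/2) ÷ ln 2 = 0.058/0.693 = 8% at 50%. With a true odds ratio of 1, estimates were 0.95 to 1.07 in every cell. Interval coverage was 93-98% throughout.

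**True odds ratio 2.5, assumed event rates.** By maximum likelihood the median estimate was 2.63 to 2.89 at N=100 and 2.58 to 2.83 at N=150. The log shifts are ln(2.63/2.5) = 0.05 to ln(2.89/2.5) = 0.14, and ln(2.58/2.5) = 0.03 to ln(2.83/2.5) = 0.12. Firth fitting with the same covariates brought the median to 2.40 to 2.50 and reduced variance at N=100.

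**Where the divergence occurs.** With nine parameters, a 10% rate, N=100 and no effect, some coefficient diverged in 41% to 56% of trials, depending on the assumed race mix and Apgar correlations. The treatment coefficient itself diverged in at most 0.6% to 1.5%.

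**Variability and error rate under no effect, N=100.** The SD of the log odds ratio was 0.49 to 1.00 with nine parameters by maximum likelihood, against 0.42 to 0.69 for Firth with arm and gestational age. That contrast changes both the covariates and the fitting method. Wald type I error was 3.8-6.2%. The likelihood-ratio test gave 6.1-7.3% with nine parameters; its Monte Carlo standard error is √(0.05 × 0.95/1500) = 0.56 points.

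**The case against.** A reader might infer that every binary outcome is over-fitted, and that the infection, hearing, PDA and MRI odds ratios will all come out too large. The documents do not support that.

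- **No event rates are given.** Over-fitting depends on event counts. Ten events per parameter is a rule of thumb, and falling below it proves nothing by itself.
- **The denominator may exceed 100.** That figure is what remains after attrition over the whole study. Infection, PDA ligation and hearing are recorded during the NICU stay, so more of the 150 may contribute. This stands, though 150 is a ceiling: deaths and the rule of one infant per multiple-birth set reduce it, and at a 10% rate instability persists at 150.
- **The planned comparison is unadjusted.** Fisher's exact and chi-square tests are unaffected, and the text does not tie the logistic model to any named outcome. This stands. The sentence does not exclude any binary outcome either.
- **There is no false signal under no effect.** Null estimates centre on 1, Wald error is near nominal, and divergence is almost all in nuisance terms. This stands. It confines the problem to failed fits, added variability and overstatement of real effects.
- **Non-collapsibility might explain the excess.** It does not. The seven-term model contains every covariate that generated the data, so its excess over 2 is small-sample bias. Non-collapsibility explains why the unadjusted estimate falls to 1.88-2.00 at rates of 10-50%, and contributes to the larger adjusted standard error (0.57 against 0.51 at 20%, no effect, N=100).
- **Dropping birth weight would lose something.** The authors raise birth weight themselves for the PDA finding. This stands, so it should not simply be deleted.

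**Conclusion.** The point holds in a limited form. For uncommon outcomes (about 10-20% or less), ordinary maximum likelihood with this covariate list is unstable at N=100. At a 10% rate, 18% of seven-term fits fail, and 41% to 56% of nine-term fits have a diverging coefficient; at 20% the seven-term figure is only 1-2%. A true odds ratio of 2.5 has a median estimate of about 2.6 to 2.9. For common outcomes the fit rarely fails and the overstatement is modest.

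These sizes rest on assumed event rates, covariate effects and coding, and on reading the plan as ordinary unpenalised logistic regression, since it names no other method. The omission of SGA needs no assumption: it is a randomisation stratum and is not among the named adjusters. All the outcomes concerned are secondary or monitored, so the primary conclusions do not depend on this. It is a cheap improvement.

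**What to change.** Replace the logistic regression sentence with one along these lines: adjusted analyses of binary outcomes will use Firth penalised-likelihood logistic regression with profile-likelihood intervals, with arm, gestational age and SGA status as the prespecified core covariates. Reporting a Mantel-Haenszel risk difference across the four randomisation strata is an acceptable alternative.

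Keep birth weight, race, gender and Apgar scores for a sensitivity model fitted the same way, with their coding stated. The unadjusted Fisher or chi-square comparison stays as it is.

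The cost is a sentence or two in the analysis section, slight shrinkage of the estimates towards no effect, and a little more analysis work. No change to recruitment or data collection is needed.
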